Complete Title: Evaluating a Marketing Campaign to Increase Participation in School Meals

Short Title: Increasing School Meal Participation

Protocol Date: July 19, 2024

NCT #: NCT06419218

Study Principal Investigator:

[name]
Stanford University
email: [contact]

Introduction

The goal of these analyses is to examine whether parental exposure to a social media campaign encouraging school meal participation increases the frequency with which children eat school lunch and school breakfast. This analysis plan pre-specifies the analyses before collecting data and therefore serves as our ex-ante planned analysis.

Study Protocol

Participants will complete a randomized controlled trial. After providing informed consent, participants will take a baseline survey programmed in Qualtrics. At the end of the survey, participants will be randomized to 1 of 2 arms: 1) school meal campaign or 2) control campaign (focused on reading, a neutral topic unrelated to school meals). In the school meal campaign arm, participants will be asked to join a private Facebook group where they will view messages about the benefits of children eating school meals. In the control arm, participants will be asked to join a private Facebook group where they will view messages about the benefits of their children reading (a neutral topic unrelated to school meals). In both arms, researchers will post messages to the private Facebook groups approximately twice per week for 6 weeks. After the 6-week campaigns end, participants in both arms will take a follow-up survey programmed in Qualtrics.

Statistical Considerations

General Principles

Primary analyses will be intent-to-treat, including all randomized participants regardless of whether they joined a Facebook group or completed the follow-up survey. Depending on the proportion of participants who join the Facebook groups, we may consider conducting secondary, per-protocol analyses including only participants who joined a Facebook group.

We will use a two-sided critical alpha of 0.05 to conduct all statistical tests. All confidence intervals presented will be 95% and two-sided.

Outcome Measures

Table 1 describes the outcome measures.

Table 1. Outcome measures

Outcome	Description	Timing of Assessment
Co-primary outcomes		

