Outcome	Description	Timing of Assessment
Child food insecurity	
Parental report of child food insecurity. Assessed with 8 items (e.g., “In the last month, did you ever cut the size of your child's meals because there wasn't enough money for food?”) Response options include “no” or “yes”; “never true”, “sometimes true”, or “often true”; “only 1 or 2 days,” “some days but not every day,” or “almost every day.” Responses of “often” or “sometimes” and “yes” are coded as affirmative (yes). Responses of “almost every day” and “some days but not every day” are coded as affirmative (yes). The sum of affirmative responses to the 8 questions in the module is the child's raw score on the scale.
 
Child food security status is assigned as follows:
 
Raw score 0-1—High or marginal food security among children
 
Raw score 2-4—Low food security among children
 
Raw score 5-8—Very low food security among children
 
Analyses will dichotomize households into those with children with high or marginal food security and those with children with low or very low food security.
	Collected in a ~10 minute survey at baseline and again at 6 weeks.

Data Preparation

To prepare the data, we will examine all scales to ensure they achieve adequate internal consistency (Cronbach's $\alpha > 0.70$), dropping items as needed to improve internal consistency. If we are unable to achieve adequate internal consistency by dropping items, we may exclude the unreliable scales from analyses (e.g., not analyze treatment effects on these outcomes).

Statistical Methods

1. Analyses of the co-primary outcomes:

- a. We will use mixed effects regression models to **evaluate the effect of the school meals campaign on children's school lunch consumption and children's school breakfast consumption**. In separate models for lunch and breakfast, we will regress usual number of school meals eaten per week on an indicator variable for trial arm (school meal campaign vs. control), an indicator variable for time period (baseline vs. follow-up) and the interaction between trial arm and time period. The treatment effect is given by the coefficient on the interaction term. We will consider linear or Poisson models, based on the distribution of the outcome and model fit. We will treat the intercept as random to account for repeated measures within participants and will include state fixed effects.

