We estimated power using G*Power 3.1.¹ No published studies have examined the effect of parent-directed school meal marketing campaigns on children's school meal consumption,² so we powered to detect a small standardized effect (Cohen's $f=0.05$, equivalent to $d=0.10$).³ We assumed 75% of the initial sample of 800 parents would complete the follow-up survey (similar retention to a previous study using similar methods⁴), yielding an analytic sample of $n=600$. Assuming $\alpha=0.05$ and a correlation among repeated measures of 0.60 (based on prior research⁵), a sample of this size would yield 80% power to detect an effect of school meal campaign on consumption of school lunch and consumption of school breakfast of $f=0.05$ or larger. Our prior studies with parents suggest that messaging interventions are likely to yield effects of this size or larger.⁶⁻⁸ Additionally, studies of child-directed school meal marketing campaigns⁹ and multicomponent interventions that include marketing^{10,11} suggest effects of this size are reasonable.

Exclusions and Outliers

We will exclude participants who do not consent or do not complete the baseline survey, as these participants will not be randomized. Primary analyses will be intent-to-treat, including all randomized participants regardless of whether they join their assigned Facebook group or complete the follow-up survey. We will also consider conducting a secondary analysis per-protocol, examining only those who joined their assigned Facebook group and completed the follow-up survey.

References

3. Cohen J. *Statistical Power Analysis for the Behavioral Sciences*. Academic press; 2013.

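### The power statement equates f = 0.05 with d = 0.10, but for the planned arm-by-time interaction f = 0.05 is a difference-in-differences of 0.20 SD; power at 0.10 SD is about 28%, not 80%

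*Combined protocol and SAP*

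**What the plan says.** Sample Size Needs reports a G*Power 3.1 calculation for a small standardised effect, "f=0.05$, equivalent to $d=0.10". On retention it says "We assumed 75% of the initial sample of 800 parents would complete the follow-up survey", "yielding an analytic sample of $n=600". It takes alpha as 0.05 and assumes "a correlation among repeated measures of 0.60". It concludes that this sample "would yield 80% power to detect an effect of school meal campaign on consumption of school lunch and consumption of school breakfast" at f = 0.05 or above. The section then supports that target by saying earlier messaging and school-meal studies make effects of at least this size plausible.

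The tested quantity is fixed in Statistical Methods 1a. The mixed model has an indicator for arm, an indicator for period (baseline or follow-up) and their product, and "The treatment effect is given by the coefficient on the interaction term". General Principles adds: "We will use a two-sided critical alpha of 0.05 to conduct all statistical tests".

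The plan does not name the G*Power test, define d, or state the allocation ratio.

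**The concern.** The conversion d = 2f belongs to a comparison of two independent means at one time point. The primary analysis tests a difference-in-differences, for which f and the treatment effect are related differently. If the software was given f = 0.05 for the interaction, the trial was sized for an effect twice the one the plan names.

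The figure d = 0.10 is the only between-group effect size the plan offers, and it applies to both co-primary outcomes. A reader will take it as the effect the trial can detect, and may judge the prior-evidence argument against it. If true power at 0.10 SD is far below 80%, a non-significant result could be taken as evidence against an effect of that size when the trial had little chance of finding it.

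**Working it through.** **Inputs from the plan.** N = 600 completers out of 800 (75% retention); correlation ρ = 0.60; two-sided alpha 0.05; 2 arms; m = 2 measurements; f = 0.05; claimed power 80%.

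**Assumptions not in the plan.** 1:1 allocation (300 completers per arm), the same outcome SD at both times, d in units of that SD, a linear model, state effects ignored.

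**1. Reproduce the plan's figure.** For the repeated-measures within-between interaction in G*Power:

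λ = f² × N × m / (1 − ρ) = 0.0025 × 600 × 2 / 0.4 = 7.5, with 1 and 598 degrees of freedom.

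Power = 78.1%, within 2 points of the stated 80%. Other choices at f = 0.05 do not come as close:

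| Calculation at f = 0.05 | Power |
|---|---|
| Within-between interaction, N = 600 | 78.1% |
| Between-factors test | 27.7% |
| Follow-up only, two groups | 23.1% |
| Effect-size option that ignores ρ | 40.9% |
| Partial-eta-squared-type option | 23.1% |
| One-sided interaction | 86.3% |
| Interaction with N = 800 | 88.5% |

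A pure pre-post time effect gives the same 78.1%, but it does not compare arms.

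**2. Convert f to the treatment effect.** Let the four cell means be 0, 0 (control, baseline and follow-up) and 0, D (campaign, baseline and follow-up), in SD units. After removing row and column means, each cell keeps ±D/4. So f = D/4:

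- D = 0.20 gives f = 0.05
- D = 0.10 gives f = 0.025

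**3. Check through the standard error.** The change-score variance is 2(1 − 0.60) = 0.8, so

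SE(D) = √(2 × 0.8 / 300) = 0.0730 SD.

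- D = 0.20: 0.20 / 0.0730 = 2.739, whose square is 7.5, matching λ in step 1. Power = Φ(2.739 − 1.96) = 78.2%.
- D = 0.10: 0.10 / 0.0730 = 1.369. Power = Φ(1.369 − 1.96) = 27.7%. The noncentral F with λ = 0.025² × 600 × 2 / 0.4 = 1.875 also gives 27.7%.

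**4. Use the baseline-only parents.** The intent-to-treat mixed model would use 800 baseline and 600 follow-up records. By maximum likelihood,

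Var(D) = 2 × [(1 − 0.36)/300 + (1 − 0.60)²/400] = 0.00507, SE = 0.0712.

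Power is 80.2% at D = 0.20 and 29% at D = 0.10.

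**5. Try other readings of d = 0.10.**

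| Reading | Power |
|---|---|
| Baseline-adjusted ANCOVA, 600 completers | 33.4% |
| All 800 followed up | 35.2% |
| d in change-score SD units | 23.1% |
| ρ = 0.90 instead of 0.60 | 78.2% |

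**6. What the design can detect, and what 0.10 SD would need.**

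- Detectable with 80% power at 600 completers: (1.96 + 0.8416) × 0.0730 = 0.205 SD.
- Completers per arm for 0.10 SD: 2 × (1.96 + 0.8416)² × 0.8 / 0.10² ≈ 1,256, or 2,512 in all. Randomised: 2,512 / 0.75 ≈ 3,350.
- In days per week, assuming an outcome SD of 1.5 to 2.1 (the plan gives none): 0.205 SD is about 0.3 to 0.4 days, whereas 0.10 SD would be about 0.15 to 0.2 days.

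**The case against.** The power sentence itself is phrased in f, and for f = 0.05 it is essentially right. The symbol d occurs once, in a parenthesis, and is not defined. Some factorial-design conventions report an interaction as half the difference-in-differences; on that scale f = 0.05 and d = 0.10 agree. The G*Power test is inferred, and a time effect would give the same number with d = 2f valid. Finally, the plan promises 95% confidence intervals, which will show what the data exclude whatever the design section says.

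The first point stands: the fault lies in the conversion, not in the 80% for f = 0.05. The half-effect reading does not fit the plan, which codes arm and period as indicators and takes the interaction coefficient as the treatment effect; that coefficient is the full difference-in-differences. A time effect is not an effect of the campaign. No comparison of arms that was tried at ρ = 0.60 comes near 80% at 0.10 SD.

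It also stands that the test and the allocation ratio are undocumented, and that misreading of a null result is a risk, not a certainty. The intervals reduce that risk but do not mend the sample-size rationale. Whether the cited studies support 0.20 SD cannot be judged from the plan.

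**Conclusion.** Wrong as written. For the planned interaction, f = 0.05 is a difference-in-differences of 0.20 SD, so the stated d is half the effect the trial is powered for. Power at 0.10 SD is about 28%, or 29% with all available records: the trial would miss such an effect about 7 times in 10. The effect detectable with 80% power is about 0.20 SD.

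This rests on the assumptions listed in the working. The most favourable alternative tried at the stated correlation gives 35%, so the conclusion does not depend on fine details. The days-per-week range depends on the assumed SD; the power figures do not. Because the sample-size justification relies on the size of this effect, the statement must be corrected.

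**What to change.** In Sample Size Needs, remove the equivalence with d = 0.10 and replace it with wording such as:

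> f = 0.05 for the arm-by-time interaction, which is a difference-in-differences of 0.20 SD (f = difference-in-differences / 4). With 600 completers and a correlation of 0.60, power is about 80% for 0.20 SD and about 28% for 0.10 SD.

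Name the G*Power test and state the allocation ratio. Then re-check, against 0.20 SD, the claim that prior studies make an effect of this size reasonable, and revise it if they do not.

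The cost is one corrected sentence, a short review of the cited evidence and a less favourable stated detectable effect. Enrolment, model and alpha are unchanged. If 0.10 SD was in fact the intended target, the alternative is to resize to about 3,350 randomised; otherwise the plan should say openly that it is not powered for 0.10 SD.
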